7.3.6. Laboratory Assessments

All protocol required laboratory assessments, as defined in Table 13), should be performed according to the Time and Events Tables (Section 7.1). Details for the preparation and shipment of samples will be provided in the SPM.

At the discretion of the investigator, additional laboratory samples may be taken as clinically necessary. If additional non-protocol specified laboratory assessments are performed at the institution's local laboratory and result in a change in subject management or are considered clinically significant by the investigator (for example SAE or AE or dose modification) the results must be recorded in the subject's eCRF.

All abnormal laboratory tests with values that are clinically significant during study participation or within 28 days after the last dose of study treatment should be repeated until the values return to within normal range or baseline or the subject starts subsequent treatment. All subjects who have a Grade 3 or 4 laboratory abnormality at time of study withdrawal must be followed until resolution to Grade 2 or less, unless it is unlikely to improve due to underlying disease or subsequent therapy.

Hematology, clinical chemistry, urinalysis and additional parameters to be tested are listed below:

Table 13 List of Clinical Laboratory Tests

Hematology			
Platelet Count		RBC Indices:	Automated WBC Differential:
Red blood cell (RBC) Count		Mean corpuscular volume (MCV)	Neutrophils
White blood cell (WBC) Count (absolute)		Mean corpuscular hemoglobin (MCH)	Lymphocytes
Reticulocyte Count		Mean corpuscular hemoglobin concentration (MCHC)	Monocytes
Hemoglobin			Eosinophils
Hematocrit			Basophils
Clinical Chemistry			
Blood urea nitrogen (BUN) or urea	Potassium	AST	Total and direct bilirubin
Creatinine	Chloride	ALT	Uric Acid
Glucose, fasting	Total carbon dioxide (CO ₂)	Gamma glutamyl transferase (GGT)	Albumin
Sodium	Calcium	Alkaline phosphatase	Total Protein
Magnesium	Phosphate		
Routine Urinalysis			
Specific gravity			
pH, glucose, protein, blood and ketones by dipstick			
Microscopic examination (if blood or protein is abnormal)			
Other tests			
PT, INR, PTT			
Testosterone (male subjects only)			
Luteinizing Hormone (LH) (male subjects only)			
Follicle stimulating hormone (FSH) and estradiol (as needed in women of non-child bearing potential only)			

7.3.7. Pregnancy Testing and Reporting

All pregnancies in female subjects and/or female partners of male subjects will be collected after the start of dosing and until the post-study visit.

The need for a screening pregnancy test depends on whether a female subject is of childbearing potential or non-childbearing potential.

If a female subject is of childbearing potential, she must have a serum Beta-human chorionic gonadotropin (β -HCG) pregnancy test performed within 7 days prior to the first dose of study treatment. Subjects with positive pregnancy test result must be excluded from the study. Subjects with negative pregnancy test result must agree to use an effective contraception method as described below during the study until 45 days or 5 half-lives (whichever is longer) following the last dose of study treatment. Additional pregnancy tests will be performed as outlined in the Times and Events Table (see Section 7.1).

Any pregnancy that occurs during study participation must be reported using a clinical trial pregnancy form. To ensure subject safety, each pregnancy must be reported to GSK within 2 weeks of learning of its occurrence. The pregnancy must be followed up to determine outcome (including premature termination) and status of mother and child. Pregnancy complications and elective terminations for medical reasons must be reported as an AE or SAE. Spontaneous abortions must be reported as an SAE.

Any SAE occurring in association with a pregnancy brought to the investigator's attention after the subject has completed the study and considered by the investigator as possibly related to the study treatment, must be promptly reported to GSK.

In addition, the investigator must attempt to collect pregnancy information on any female partners of male study subjects who become pregnant while the subject is enrolled in the study. Pregnancy information must be reported to GSK as described above.

7.4. Pharmacokinetics

For subjects enrolled in Part 1, dose escalation Cohorts 1-4, blood samples for analysis of GSK2849330 concentrations will be collected on Day 1: pre-dose and at 1 hour and 6 hours after the end of infusion and at Day 8, Day 15, and Day 29 after the first dose of GSK2849330. If a subject's duration of infusion is 3 hours or longer, the 6-hour time point is optional. On days of dosing, the sample will be drawn pre-dose. Additionally the first subject in Cohort 1 will have PK samples taken at 24 hour (Day 2) and 72 hour (Day 4) after the end of infusion.

For cohorts enrolled under Amendment 1 of this protocol, more frequent PK samples will be collected on Day 1: pre-dose and at 1 hour, 6 hours and 24 hours after the end of infusion;. Pre-dose samples will also be collected on Day 4, Day 8, and weekly through Day 57 with additional 1 hour post-dose samples collected on Days 29 and 57. Pre-dose samples will also be collected on Day 71, Day 85, and every 12 weeks thereafter.

For all subjects in the Part 1 PK/PD cohorts, blood samples for analysis of GSK2849330 concentrations will be collected on scheduled dosing Days 1: pre-dose and at 1 hour, 6 hours and 24 hours after the end of infusion. Pre-dose samples will also be collected on Day 4, Day 8, and weekly through Day 57 with additional 1 hour post-dose samples collected on Days 29 and 57. Pre-dose samples will also be collected on Day 71, Day 85 and every 12 weeks thereafter.

For the molecularly defined tumor histology groups in Part 2, blood samples for analysis of GSK2849330 concentrations will be collected on Day 1: pre-dose and at 1 hour after the end of infusion; and pre-dose on Day 15, Day 29, Day 43, Day 57, Day 71, Day 85, and every 12 weeks thereafter.

For all subjects (Part 1 and Part 2), if treatment continues beyond 1 year, samples will be collected every 24 weeks. An additional PK sample will also be taken at the Follow-up visit (28 days after the last dose of study treatment), and/or the Post study visit (45 days or 5 half-lives [whichever is longer] after the last dose of study treatment). Unless stated otherwise, on days of dosing PK samples will be drawn pre-dose.

See the Time and Events Tables Section 7.1 and the SPM for additional details on the PK sample timing.

7.4.1. Blood Sample Collection for Pharmacokinetics

Blood samples for PK analysis of GSK2849330 will be collected at the time points indicated in the Time and Events Tables (Section 7.1). Each PK sample should be collected as close as possible to the planned time relative to the dose (i.e., time zero) administered to the subject on PK days. The actual date and time of each blood sample collection will be recorded.

Once preliminary PK data have been reviewed, the planned sample collection times may be revised and provided to sites in writing. Changes in PK sample collection times will not constitute a protocol amendment.

Details of PK blood sample collection (including volume to be collected), processing, storage and shipping procedures are provided in the SPM.

7.4.2. Pharmacokinetic Sample Analysis

Plasma analysis will be performed under the management of Bioanalytical Science and Toxicokinetics, Drug Metabolism and Pharmacokinetics (DMPK), GSK. Concentrations of GSK2849330 will be determined in plasma samples using the currently approved analytical methodology. Raw data will be stored in the GLP Archives, GSK.

7.5. Immunogenicity

7.5.1. Blood Sample Collection

Serum samples for determination of anti- GSK2849330 antibodies will be taken from all subjects in this study at the time-points specified in the Time and Events Tables in Section 7.1.

7.5.2. Sample Analysis

Samples will be analyzed for the presence of anti-GSK2849330 antibodies using a validated immunoelectrochemiluminescence assay. The assay involves screening, confirmation and titration steps (tiered-testing approach). Confirmed positive samples will be titrated to obtain the titer of the anti-GSK2849330 antibodies. Further antibody characterization may be performed, if needed. Results will be reported at the end of the study. Details on sample preparation, storage and analysis will be given in the SPM.

7.6. Translational Research

Unless stated otherwise, these investigations may be performed irrespective of whether a response to GSK2849330 is observed.

Comparative examination of pre-dosing profiles of participants may uncover known or novel candidate biomarkers/profiles which could be used to predict response to treatment with GSK2849330 or provide new insights into cancer and medically related conditions. Comparative examination of post-dosing profiles with pre-dosing profiles may yield known and novel candidate biomarkers/profiles and new insights which relate directly or indirectly to the mechanism of action of GSK2849330.

All samples may be retained for a maximum of 15 years after the last subject completes the study.

Novel candidate biomarkers and subsequently discovered biomarkers of the biological response associated with cancer or medically related conditions and/or the action of GSK2849330 may be identified by application of:

- DNA/gene, RNA, protein and cell population analysis of tumor/skin tissue.
- Circulating cell free-DNA analysis of blood/plasma.
- Circulating/peripheral biomarkers
 - Cytokines and Angiogenic Factors (CAF) analysis of plasma
 - Proteome analysis of plasma
 - Complement CH50 analysis of serum
 - Peripheral blood mononuclear cell (PBMC) count analysis of whole blood

RNA transcriptome research and/or RNA expression research on whole or a subset of RNA species are included as relevant for the study.

7.6.1. Tumor Biomarker Analysis

7.6.1.1. Tumor Tissue for Pre-screening Assessments and Exploratory Research

Tumor tissue taken from a metastatic site (preferably) or obtained at the time of primary cancer diagnosis (biopsy or from definitive surgery) is required to be submitted for analysis to one or more of the central laboratories, including Ventana Medical Systems to determine HER3 and NRG1 expression. If archival tumor tissue is not available, a fresh biopsy using a procedure that is safe for the subject is required for HER3 and NRG1 testing.

Refer to the SPM for further details on tumor tissue sample requirements preparation and shipping.

Additional exploratory research may include the evaluation of intra-tumoral molecular profiles (to include RNA, DNA/gene, protein, and cell populations) that may uncover known or novel candidate biomarkers/profiles that could be used to predict response to GSK2849330 or possibly glean biological information into its mechanisms of action.

Histological features may be evaluated to include but are not limited to the enumeration of cell type populations such as lymphocytes.

7.6.1.2. Tumor Biopsies

Every effort should be made to collect pre- and on-treatment tumor biopsies using a procedure that is safe for the subject. Image guidance has been shown to significantly increase the probability of success in obtaining tumor biopsies and is required for all percutaneous pre- and on-treatment biopsies in this study (with the exception of melanoma skin lesions or cutaneous metastases of other solid tumors).

Tumor biopsies are optional for subjects in the dose escalation cohorts, but strongly encouraged. All subjects enrolled in PK/PD cohorts in Part 1 and in each of the molecularly defined tumor histology groups in Part 2 must agree to pre and on-treatment tumor biopsies (using a procedure that is safe for the subject) for assessment of PD effect. GSK will closely monitor and evaluate the collection of evaluable biopsies and will notify the participating centers of any change to the collection requirements for any or all groups.

Tumor biopsies for PD analyses will be collected at the time points listed in the Time and Events Tables Section [7.1](#).

Tumor biopsies should be obtained upon disease progression, using a procedure that is safe for the subject, if the subject provides consent, and if the tumor is in a biopsy-accessible location. Once preliminary PK and PD data have been reviewed, the planned tumor biopsy collection times may be revised and provided to sites in writing. Changes in sample collection times will not constitute a protocol amendment.

Biopsies may be analyzed for genetic markers (mutations in genes to potentially include but not limited to PIK3CA, PTEN, and BRAF), DNA, RNA or protein levels that may indicate a PD response, or correlate with a tumor response, to GSK2849330. Protein levels that may be analyzed include, but are not limited to, markers of the HER3 pathway such as HER3, phospho-HER3 and HER3 ligands (neuregulins); markers of cell proliferation such as Ki67; markers of ADCC such as perforin and granzyme B; markers of the CDC pathway; and markers of tumor resistance such as the PTEN protein. Additional analyses may include the evaluation of histological features to include but are not limited to the enumeration of cell type populations such as lymphocytes.

Details on tumor biopsy collection, processing, storage and shipping procedures are provided in the SPM.

7.6.2. Skin Biopsies

For subjects in Part 1 of the study, every effort should be made to collect pre- and on-treatment skin biopsies for analysis of RNA or protein levels that may indicate a PD response to GSK 2849330. Protein levels that may be analyzed include, but are not limited to, markers of the HER3 pathway such as HER3 and phospho-HER3.

All subjects enrolled in dose escalation and PK/PD cohorts in Part 1 must agree to pre and on-treatment skin biopsies for assessment of PD effect.

Refer to Time and Events Tables in Section 7.1 for details on time points.

Details on skin biopsy collection, processing, storage and shipping procedures are provided in the SPM.

7.6.3. Blood Samples

Blood-based markers have the important advantage that specimens are readily available, simple to prepare and store, and can be taken prior to and during treatment. This allows for the assessment of predictive markers based on the baseline evaluation as well as markers of activity and resistance based on changes that occur during treatment.

Blood samples will be collected for analysis of potential surrogate markers of GSK2849330 activity. These analyses may include, but are not limited to measurement of specific blood proteins and cell populations (e.g., PBMCs: CD16, CD56, CD69, CD107, CD19, CD8, CD4, CD3, CD14), complement activity (e.g., CH50), inflammatory cytokines (e.g., IFN γ , TNF α , IL-2, IL-6), growth factors, soluble HER3, or mutations in circulating free tumor DNA (Refer to Section 7.6.3.1).

Blood samples drawn for investigating both predictive and PD biomarkers will be by study part and subject cohort or group:

Details on sample collection, processing, storage and shipping procedures are provided in the SPM.

7.6.3.1. Circulating Cell-free DNA (cfDNA) Analysis

Tumor-specific cfDNA levels detected in plasma or serum have been found to correlate with increasing tumor burden and decline following therapy. Furthermore, cfDNA in cancer subjects can harbor many genetic alterations (mutations, microsatellite alterations, aberrant methylation), which are generally consistent with the tumor. Thus, tumor-specific circulating cfDNA has the potential to be a useful biomarker of therapeutic response as well as offering a less invasive blood based technique for identifying and selecting subjects for certain treatments. Given the promise of cfDNA blood based test for subject selection, this test will be explored to determine whether mutations in cfDNA that may include but are not limited to PIK3CA, PTEN, and BRAF, correlate with the mutations in the tumor. This test will also be explored to correlate increasing cfDNA levels with increasing tumor burden. These mutations will be specific to the primary tumor types enrolled in the study.

7.6.3.2. Cytokines Analysis

A panel of inflammatory cytokines which may include but are not limited to IFN γ , TNF α , IL6, IL2, and MCP-1 will be evaluated in plasma and correlated with clinical outcome of treatment with GSK2849330.

7.7. Pharmacogenetics (PGx)

An important objective of the clinical study is PGx research. Participation in PGx is optional but all subjects who are eligible for the clinical study will be given the opportunity to participate. Subjects may decline participation without effect on their medical care or care during the clinical study. A separate consent signature is required for PGx research.

Subjects who provide consent will have a blood sample taken for analysis. The presence/absence of genetic variations in selected candidate genes, such as but not limited to the FC γ receptor family, in DNA from blood may be analyzed to determine their relationship with response (safety, tolerability, PK and efficacy to treatment with GSK2849330).

Information regarding PGx research is included in [Appendix 8](#). The IRB/EC and, where required, the applicable regulatory agency must approve the PGx assessments before these can be conducted at the site. The approval(s) must be in writing and will clearly specify approval of the PGx assessments (i.e., approval of [Appendix 8](#)). In some cases, approval of the PGx assessments can occur after approval is obtained for the rest of the study. If so, then the written approval will clearly indicate approval of the PGx assessments is being deferred and the study, except for PGx assessments, can be initiated. When PGx assessments will not be approved, then the approval for the rest of the study will clearly indicate this and therefore PGx assessments will not be conducted.

7.8. Evaluation of Anti-Cancer Activity

Disease assessment may include imaging (e.g., CT scan, MRI, bone scan, plain radiography) and physical examination (as indicated for palpable/superficial lesions). Disease assessment will be completed within 4 weeks prior to the first dose of GSK2849330, then every 8 or 9 weeks thereafter, and at the final study visit. See the Time and Events Tables (Section 7.1) for the schedule of assessments of anti-cancer activity. Assessments must be performed on a calendar schedule and should not be affected by dose interruptions/delays. For post-baseline assessments, a window of ± 7 days is permitted to allow for flexible scheduling. If the last radiographic assessment was more than 8 weeks prior to the subject's withdrawal from study, progressive disease (PD) has not been documented, and the subject has not started subsequent anti-cancer therapy, a disease assessment should be obtained at the Follow-up visit or the Post-study visit.

In addition to the above, a MRI with contrast should be considered to rule out the presence of brain metastases. CT scans with and without contrast may be performed if a MRI is contraindicated or otherwise unavailable.

For purposes of determining futility, disease progression and response evaluations will be determined according to the definitions established in the Response Evaluation Criteria in Solid Tumors (RECIST 1.1) [Eisenhauer, 2009] (see Appendix 5). Exploratory assessment of response according to immune-related response criteria (Appendix 6) and mRECIST (Appendix 7) [Lencioni, 2010] should also be recorded. Subjects whose disease responds (either CR or PR) should have a confirmatory disease assessment performed at least 4 weeks after the date of assessment during which the response was demonstrated. More frequent disease assessments may be performed at the discretion of the investigator. To ensure comparability between the baseline and subsequent assessments, the same method of assessment, the same technique and the same radiologist should be used when assessing response. Images should be retained until study completion to facilitate central review if requested. Tumor markers should be followed serially per institutional guidelines and recorded in the eCRF where part of standard practice.

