3. INVESTIGATIONAL PLAN

3.1. Discussion of Study Design

Protocol waivers or exemptions are not allowed. Therefore, adherence to the study design requirements, including those specified in the Time and Events Tables (Section 7.1) are essential.

Supplementary study conduct information not mandated to be present in this protocol is provided in the accompanying Study Procedures Manual (SPM). The SPM will provide the site personnel with administrative and detailed technical information that does not impact subject safety.

This is a Phase I, FTIH, open-label, multi-center, dose-escalation study of the anti-HER3 antibody, GSK2849330, in subjects with advanced solid tumors expressing HER3 (see Inclusion Criteria 3 and 9). The study will be conducted in two parts as depicted below.

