3.9.4. Dose Modifications

In the event of a toxicity that meets the guidelines for DLT (Section 3.3.1) or is otherwise considered to be clinically significant by the treating physician, treatment will be stopped and supportive therapy administered as clinically indicated. If clinically significant drug-related toxicity is present, treatment should be delayed until the toxicity resolves (with or without supportive therapy) to baseline or \leq Grade 1. If the toxicity does not resolve to \leq Grade 1 or baseline within 2 weeks, withdrawal from the trial is recommended unless otherwise agreed to by a GSK Medical Monitor and the investigator based on evidence of clinical benefit.

For subjects enrolled in the 30 mg/kg weekly dosing cohort, the dosing frequency may be reduced to every 2 weeks at the discretion of the investigator for a toxicity that does not automatically necessitate a dose reduction.

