6.3. Permanent Discontinuation from Study Treatment

Subjects will receive study treatment until disease progression, death or unacceptable toxicity, including meeting stopping criteria for liver chemistry defined in Section 3.8.1. In addition, study treatment may be permanently discontinued for any of the following reasons:

- major deviations(s) from the protocol
- request of the subject or proxy (withdrawal of consent by subject or proxy)
- investigator's discretion
- a dose delay for toxicity of > 2 weeks unless the investigator or GSK Medical Monitor agree that further treatment may benefit the subject
- intercurrent illness that prevents further administration of study treatment
- subject is lost to follow-up, or the study is closed or terminated.

The primary reason study treatment was permanently discontinued must be documented in the subject's medical records and eCRF.

If the subject voluntarily discontinues from treatment due to toxicity, 'AE' will be recorded as the primary reason for permanent discontinuation on the eCRF.

Once a subject has permanently discontinued from study treatment, the subject will not be allowed to be retreated.

All subjects who discontinue from study treatment will have safety assessments at the time of discontinuation and during post-study treatment follow-up as specified in Time and Events Tables (see Section 7.1).

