12. Blood samples for analysis of GSK2849330 concentrations will be collected on Day 1: pre-dose and at 1 hour (\pm 15-minute window), and 6 hour (\pm 1-hour window) after the end of infusion. If a subject's duration of infusion is 3 hours or longer the 6-hour time point is optional. Additional PK samples will be collected at Day 8, Day 15, and Day 29. Additional PK samples will also be taken every 12 weeks from the first dose within 1 year of starting treatment and if treatment continues after 1 year samples will be collected every 24 weeks. An additional PK sample will also be taken at the Follow-up and Post-study visits. Unless stated otherwise, on days of dosing sample will be drawn pre-dose. For the first subject in Cohort 1, additional PK samples will be taken at 24 hours (Day 2 [\pm 8-hours window]) and at 72 hours (Day 4 [\pm 24-hour window]) after the end of infusion of the first dose of GSK2849330.
13. To be conducted in male subjects only.
14. Whole blood for soluble markers from plasma, serum, and/or cellular markers. Blood samples will be collected on Day 1: pre-dose and at 1 hour (\pm 15-minute window) and 6 hours (\pm 1-hour window) after the end of infusion. If a subject's duration of infusion is 3 hours or longer the 6 hour time point is optional. A pre-dose blood sample should be collected on Day 8, Day 15 and Day 29 for all cohorts. An additional sample will also be collected at progression.
15. For any subjects receiving a weekly dosing schedule, the study treatment dosing window is \pm 2 days. The study treatment dosing window for all other dosing schedules (e.g., an every 2 week or every 3 week dosing schedule) is \pm 3 days. If dosing does not occur on the intended day, all other assessments/subsequent visits should be changed accordingly relative to when the dose was received. Subsequent cohorts may receive different dosing schedules use the appropriate Time and Events Table as applicable.
16. After the first treatment period, immunogenicity samples will be collected every 12 weeks from the first dose within one year of treatment. If treatment continues after 1 year, samples will be collected every 24 weeks. An immunogenicity sample must be collected at both the Follow up and the Post-study visit.
17. It is preferred that the PGx sample be taken pre-dose on Day 1; however, it may be obtained anytime after informed consent has been given for PGx research.

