12. Blood samples for analysis of GSK2849330 concentrations will be collected on Day 1: pre-dose and at 1 hour (\pm 15-minute window), after the end of infusion, and pre-dose on Day 15, Day 29, Day 43, Day 57, Day 71, Day 85, and every 12 weeks thereafter. If treatment continues after 1 year, samples will be collected every 24 weeks. An additional PK sample will also be taken at the Follow-up or Post-study visits. Unless stated otherwise, on days of dosing sample will be drawn pre-dose.
13. To be conducted in male subjects only.
14. Whole blood for soluble markers from plasma, serum, and/or cellular markers. Blood samples will be collected on Day 1: pre-dose and at 1 hour (\pm 15-minute window) and 6 hours (\pm 1-hour window) after the end of infusion. If a subject's duration of infusion is 3 hours or longer, the 6-hour time point is optional. A pre-dose blood sample should be collected on Day 8, Day 15 and Day 29 for all cohorts. An additional sample will also be collected at progression.
15. For the subjects receiving a weekly dosing schedule, the study treatment dosing window is \pm 2 days. The study treatment dosing window for all other dosing schedules (e.g., an every 2-week or every 3-week dosing schedule) is \pm 3 days. If dosing does not occur on the intended day, all other assessments/subsequent visits should be changed accordingly relative to when the dose was received.
16. An immunogenicity sample must be collected at the Follow-up and Post-study visits.
17. It is preferred that the PGx sample be taken pre-dose on Day 1; however, it may be obtained anytime after informed consent has been given for PGx research.
18. See Section 7.8 and collect all tumor markers applicable for the subject's primary tumor type.
19. Confirmatory assessments will occur at least 4 weeks after assessments demonstrating CR or PR. Confirmatory assessments may be conducted at a subject's next regularly scheduled visit as appropriate.
20. A blood sample for select serum safety markers (including but not limited to TNF alpha, IL-6, and tryptase) should be drawn within 24 hours of suspected infusion-related reactions.
21. For subjects who discontinue the study prior to disease progression, disease assessment must be performed either at the Follow-up visit or at the Post-Study visit prior to the start of any subsequent anticancer therapy.
22. Assessments to be performed weekly while receiving weekly dosing and bi-weekly if switched to a bi-weekly dosing regimen.

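### Protocol Section 7.8 fixes disease assessments to the calendar, but footnote 15 of Tables 7-12 moves all assessments with a delayed dose, so scan timing can come to depend on tolerability

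*Protocol*

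**What the plan says.** Protocol Section 7.8 governs disease assessment. After baseline, scans are due "then every 8 or 9 weeks thereafter, and at the final study visit". On delays it says: "Assessments must be performed on a calendar schedule and should not be affected by dose interruptions/delays". On tolerance it says: "For post-baseline assessments, a window of ± 7 days is permitted to allow for flexible scheduling". It also sends the reader to the Time and Events tables in Section 7.1 for the schedule.

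Footnote 15 appears in each of those tables: Tables 7 and 8 (Part 1 escalation), 9, 10 and 11 (PK/PD cohorts) and 12 (Part 2). In all six it reads: "If dosing does not occur on the intended day, all other assessments/subsequent visits should be changed accordingly relative to when the dose was received". Disease assessment is a row in every one of these tables, due every 8 weeks, or every 9 in Table 11. The row gives no date from which to count. The footnote makes no exception for imaging.

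Delays are foreseen. Section 3.9.4 says: "If clinically significant drug-related toxicity is present, treatment should be delayed until the toxicity resolves". Section 6.3 lists, among the possible reasons for permanent discontinuation, "a dose delay for toxicity of > 2 weeks unless the investigator or GSK Medical Monitor agree that further treatment may benefit the subject". A delay of up to 2 weeks therefore needs no special agreement.

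**The concern.** The two instructions cannot both be followed once a dose is late. One keeps the scan where it was; the other moves it.

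The date of a documented progression or response is the date of the scan that shows it. If scans slide with doses, subjects with more toxicity are scanned on a different grid from subjects with less. The quantities exposed are:

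- **Progression dates**, and so PFS (exploratory in Part 2).
- **Best response**, the one efficacy summary table that the SAP plans (Table 10.1).
- **Timing of response data** for the Part 2 futility checks in Protocol Section 13.6.2, which are applied as enrollment proceeds.
- **Time on treatment**, because Section 6.3 continues treatment until progression.

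Nothing downstream would correct a shift. SAP Sections 8.1 and 9.2.8 report data by nominal visit and apply no assessment windows.

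**Working it through.** The documents state no figure on this point, so there is none to reproduce. The check compares the two scan grids.

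**Inputs.** Interval 56 days (63 in Table 11) and window ±7 days, from Section 7.8 and the tables. Delay of 14 days, from Sections 3.9.4 and 6.3.

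**First scan under footnote 15.** Planned day 56, permitted days 56 − 7 = 49 to 56 + 7 = 63.

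- 7-day delay: 56 + 7 = day 63, still inside.
- One 14-day delay: 56 + 14 = day 70, outside.
- Two 14-day delays: 56 + 28 = day 84, outside.
- Table 11, one 14-day delay: 63 + 14 = day 77, against permitted days 56 to 70, outside.

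Under Section 7.8 the shift is 0 in every case.

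**Who is documented later and who earlier** (one 14-day delay, carried forward; calendar scans at days 56, 112, ...; shifted scans at 70, 126, ...):

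| Progression arises | Calendar scan | Shifted scan | Difference |
|---|---|---|---|
| by day 56 | 56 | 70 | 14 days later |
| days 56-70 | 112 | 70 | 42 days earlier |
| days 70-112 | 112 | 126 | 14 days later |

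The pattern of the last two rows repeats in each later interval.

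**Mean effect in delayed subjects.** The documents give no time-to-progression figure. I assume exponential times with medians M of 61 to 183 days, so S(t) = exp(−t·ln 2 / M). The mean detection day is the sum over scans of (gap before the scan) × S(previous scan). For a single shift of d days this gives

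shift = d − 56 × S(56) × [1 − S(d)] / [1 − S(56)].

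For M = 61 and d = 14: S(56) = 0.5292 and S(14) = 0.8529, so the shift is 14 − 56 × 0.5292 × 0.1471 / 0.4708 = 14 − 9.26 = 4.74 days.

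| Assumed median (days) | Progressed by day 56 | One 14-day delay | 28 days in total before first scan | 14 days in every interval |
|---|---|---|---|---|
| 61 | 47.1% | +4.74 | +10.84 | +8.64 |
| 91 | 34.7% | +3.35 | +7.78 | +8.11 |
| 122 | 27.3% | +2.57 | +6.01 | +7.83 |
| 183 | 19.1% | +1.76 | +4.15 | +7.56 |

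Shifts are in days. The mean is later in every scenario, but well below the full length of the delay.

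**Best response.** Protocol Appendix 5 grants stable disease only if the criteria are met at least 8 weeks after first dose. A subject stable at a day-56 scan who progresses by day 70 has stable disease as best response on the calendar grid and progressive disease on the shifted grid.

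**The case against.** The strongest reply is that Section 7.8 already settles the matter. It is the section on disease assessment, it is mandatory, and it addresses dose delay by name. Footnote 15 is a general note on dosing windows, and its marker sits on the infusion row; the disease-assessment row carries notes 3, 19 and 21. On that reading the specific rule is an exception to the general one.

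This is a reasonable reading, but no text states it. The footnote speaks of "all other assessments/subsequent visits should be changed accordingly relative to when the dose was received", and Section 7.8 itself points to the tables for the schedule. A site working from its visit table has an explicit instruction to move the scan. The objection does show that later detection occurs only where a site follows the footnote, and the documents do not show which reading sites used.

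Four stronger readings are tempting and are not supported:

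- *That Section 3.1 makes the tables prevail.* It calls for "adherence to the study design requirements, including those specified in the Time and Events Tables". That includes the tables among the requirements; it does not rank them above Section 7.8.
- *That progression is dated 2 to 4 weeks late in every delayed subject.* That holds only for progression already present when the planned scan was due. Some later progressions are found sooner, and a total shift of 7 days or less stays inside the Section 7.8 window.
- *That duration of response lengthens with toxicity.* SAP Section 11 runs it from first documented response to first documented progression or death. A delay before the response moves both scan dates equally. Only a delay between response and progression can lengthen it.
- *That dose comparisons are materially distorted.* Protocol Section 13.5.1 plans no formal comparison between dose levels. SAP Section 11 describes an abbreviated efficacy analysis after early stopping, and its displays include no PFS output.

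Section 7.8 also allows more frequent assessments at the investigator's discretion, which tempers the worry about undetected progression.

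**Conclusion.** The contradiction is real, stands in the current text and runs through all six tables. Where footnote 15 is followed, a 14-day delay puts the first scan on day 70, outside the ±7-day window, and progression present by day 56 is documented up to 14 days late; after two such delays, up to 28 days.

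Averaged over delayed subjects, one 14-day delay moves detection 1.8 to 4.7 days later. That range rests on exponential progression times, the assumed medians, scans exactly on schedule, and a shift that carries forward to all later scans. The individual-level figures need only the documents' own intervals.

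The weight is modest. PFS is exploratory, duration of response is only listed, and best response is summarized descriptively. It is still worth correcting, because scan timing would otherwise depend on tolerability and no analysis rule repairs that afterwards.

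**What to change.** Reconcile the two passages. In footnote 15 of Tables 7-12, after the instruction to move other assessments, add: *except disease assessment, which stays on the calendar schedule counted from first dose, with the ±7-day window in Section 7.8*. This carries out the rule that Section 7.8 already states and supplies the anchor date that the table rows lack.

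Leave tumor markers out of the clause. Section 7.8 leaves their follow-up to institutional guidelines, so binding them to the calendar would be a new rule.

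The cost is one clause in six footnotes. The planned scan schedule is unchanged; some scans will fall on a day without dosing.
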